Upon completing the pharmacokinetics trial, the intervention phase will begin. Participants will be provided a 2-week supply of GTE-rich or placebo confections. They will be advised to consume 6 confections/ every day (2 confections/meal; 1 g GTE/d) for the following 4-wk. After 2 wk of the intervention phase, participants will complete a 3-day diet record and return for their third study visit. At this visit, fasting blood will be collected. Participants will then receive their final 2-wk supply of confections. After 4 wk, participants will complete a final 3-d diet record and perform the sugar probe test once again as described above. During each study visit, participants will have access to drinking water and use of the restroom as needed.

Sugar Probe Test. On the morning of testing at wk 0 and 4, participants will arrive at the study center after abstaining from food and only consuming water for 10-12 hours. A sugar probe test will be conducted as described (73). Upon arrival, participants will be asked to empty their urinary bladder. Subsequently, they will then be asked to ingest a drink containing 40 g sucrose, 5 g lactulose, 1 g mannitol, and 1 g sucralose dissolved in water (500 mL). Within 2-hours after ingesting the sugar test beverage, participants will be asked to consume an additional 500 mL of water. Additionally, participants will be provided with standardized sucrose-free meals during the 24-h period. All foods consumed during the 24-hour period will be free of artificial sweeteners. Urine will be collected from 0-5 and 6-24 hours in sterile containers. For each urinary collection period, participants will be provided 2-L urine collection bottles and a Styrofoam cooler with ice packs to store collected urine until they return their samples the next day.

Pharmacokinetics Trial. Within 3-d after completing the first sugar probe test, participants will return to the study center to perform a 12-h pharmacokinetics trial. At least 3-d prior to the pharmacokinetics trial, participants will abstain from polyphenol-rich foods and drinks, including any type of tea, coffee, fruits, fruit juices, any chocolate (dark, milk), nuts, legumes (soy), and wine. Participants will arrive to the study center after abstaining from food and only consuming water for 10-12 hours. Participants will be provided a 15-min rest period, prior to the first blood collection. During the rest period, the participants will sit in a phlebotomy chair and a flexible catheter will be inserted into a forearm vein by a trained phlebotomist. After a 15-min sitting rest period, a blood sample will be obtained from a 3-way stopcock connected to the end of the catheter. Blood will be collected with a syringe and transferred to appropriate tubes for processing and subsequent determination of biochemical measurements. Following the first blood collection, participants will consume 3 GTE-rich confections (0.5 g GTE). Blood samples will be collected at 0 (prior to ingestion), 0.25, 0.5, 1, 2, 3, 5, 8, 10, and 12 h. Additionally, urine will be collected between 0-4, 4-8, 8-12, and 12-24 h. During the 12 h trial period, participants will be able to freely move and walk around if they choose to, as long as they stay in close proximity to the study center. We will provide a dedicated office space for participants to sit down in between blood draws. If the participant chooses to move around, we will wrap their arm with a bandage to minimize any risks and ensure the catheter stays in place to prevent the need to insert a needle again. Additionally, a person of the research team will escort and monitor the participant if they choose to move around the study center. After each blood sample is obtained, the catheter will be flushed with saline to prevent the formation of clots and to minimize the likelihood of having to insert a needle again. At 4 hours, each participant will be provided with a standardized polyphenol-free meal. A trained phlebotomist will perform all cannula insertions, needle sticks, and blood collections. After the 12 h trial, participants will be provided with a light snack (e.g. granola bar) and prepared standardized polyphenol-free meals to consume for the remainder of the 24-h urine collection period. Participants will also be provided with a 2-wk supply of GTE-rich or placebo confections. Participants will be advised to consume 6 confections each day (2 per meal; 1 g GTE/d) for the entire 4-week intervention study. Participants will be contacted periodically by email, text, or phone, by research personnel to provide polite reminders to enhance study compliance.

Intervention Phase / Test Confections. After completing the pharmacokinetics trial, participants will partake in a 4 wk intervention. Participants will be block randomized to receive a GTE-rich or placebo (no GTE containing) confection. Confections will be low carbohydrate and low calorie. Each serving (6 g) provides <15 kcal, while delivering 1 g of decaffeinated GTE. The catechin profile (82% catechins (w/w); 63% EGCG, 18% EGC, 10% ECG, 9% EC) is similar to that of freshly brewed green teas. Sucrose will be the main carbohydrate source because sugar alcohols alter microbiota composition (66) and would confound interpretation. Decaffeinated GTE was chosen to minimize potential side effects to prevent excess caffeine consumption or caffeine/drug interactions that could result during comorbidity management of metabolic conditions. Placebo confections will be identical to GTE-rich confections, but without GTE. Confections will be packaged in single-serve, oxygen impermeable containers, and coded for study blinding. Participants will be asked to store the confections in the refrigerator to maintain quality and freshness.

Participants will be asked to consume 6 confections each day (2 with each meal) for 4 weeks. Consumption of 6 GTE-rich confections is equivalent to delivering 1 g GTE/d. Participants will receive a 2-wk supply of confections after completing the pharmacokinetics trial. Halfway through the intervention (wk 2), participants will visit the study center in a fasted state (10-12 h). Participants will return any leftover confections. After a 5 min stabilization period, a single fasting blood sample will be collected following procedures stated above. After collecting blood, the participants will be provided the final 2-wk supply of confections. At the conclusion of the intervention phase (wk 4), participants will perform a second sugar probe test. Compliance will be evaluated based on the number of confections returned throughout the study.

Sampling Handling. During the pharmacokinetics trial, at each time point, a blood sample (20 mL; 1.4 tablespoons x 10 time points = 200 mL or 0.85 cups) will be collected into evacuated blood collection tubes. Collecting a total of 200 mL or 0.85 cups at the pharmacokinetics trial is necessary to ensure adequate amount of plasma for each time point to accurately analyze the green tea catechin metabolites over the 12-hour period. During blood collection, participants may feel an initial pain when inserting the needle, bruising around the insertion area, lightheadedness, or fainting, which are common when donating blood. However, we do not foresee any additional significant risks for collecting this amount of blood over 12 hours, other than the risks stated previously.

Throughout the span of the study (~6-8 weeks in duration depending on participant/investigator availability) which consists of one acute ingestion of GTE-rich confections, a blood collection at wk 2 and 4, and 1 screening day, we will be collecting a total of ~255 mL or ~1.08 cups) of blood. Urine will be collected in provided containers (VWR) containing 10% thymol to inhibit bacterial growth. Feces will be collected using a commercial commode specimen collection system (Fisher Scientific). Briefly, the collection kit consists of the necessary materials (e.g. disposable spatula, gloves, waste bag) for participants to easily and hygienically collect their stool without contaminating the sample or themselves. We will provide participants with coolers with ice to store their fecal samples for up to 24-h after collection. We will then have the participants return their fecal samples to the study center or coordinate with study personnel to meet at a public and mutual location to return their samples within 24-h after collection. Volumes of urine will be recorded and fecal mass and observations will be recorded based on the Bristol Stool Chart (85).

During each blood collection, plasma and white blood cells will be obtained by centrifugation, and then transferred to cryogenic storage tubes. Serum samples will be obtained by allowing the blood to clot, followed by centrifugation and transfer to cryogenic storage tubes. Tubes will be

stored at -80° C until analysis can be completed. Analyses will include plasma glucose, insulin, triglyceride, total cholesterol, catechins (EGCG, ECG, EGC, EC), catechin-metabolites (e.g. valerolactones, catechin-derivatives), C-reactive protein, myeloperoxidase, pro-inflammatory gene expression and serum endotoxin and ALT. Urine will be stored at -80°C until analysis can be completed. Analysis from urine will include catechins, catechin-metabolites, sucrose, mannitol, lactulose, sucralose, and creatinine. Fecal samples will be stored at -80°C until analysis can be completed. Feces analysis will include microbiota composition and calprotectin. Remaining plasma, serum, urine, and fecal samples not used for these analyses will be archived for 5 years at -80 C in the event we decide to measure additional inflammatory, antioxidant, or microbiota related markers. Appropriate notation has been made in the informed consent to alert participants that we will be archiving specimens and that they have the right to refuse our use of these specimens for future analyses. Lastly, approval from OSU IRB will be sought via a protocol amendment prior to the analysis of any additional biomarkers not specified herein.

Privacy/Confidentiality. For all data and records that are a part of this study, a number (i.e. code) will be assigned to each participant, and will only be available to research personnel. Any records containing the names of participants will be stored in a locked filing cabinet or on a password protected computer in the PI's laboratory or office. Research personnel under the supervision of the PI and the PI himself will be the only individuals that have access to this information. The names of participants will not be used for publication in any form. The records will be maintained until the data are published, up to a maximum of five years. All archived samples will be coded, but the key linking the code to each participant's identifiable information will have been destroyed. In addition, participants will be instructed that their participation in this study is voluntary and that they may withdraw at any time without prejudice. Data (food records and biochemical values) obtained from this study will be stored on a computer in the PI's laboratory. In addition, a backup of digital data will be stored on the PI's computer in his office. Both computers are password protected and both doors are locked when work areas are not in use.

E. Internal Validity

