
Power Calculation and Data Analysis. A power calculation was performed using serum endotoxin (lipopolysaccharide; LPS) as the primary outcome. Studies in obese (44, 67, 68) adults and individuals with metabolic syndrome (69, 70) show increased serum LPS or LPS-binding protein compared to healthy controls. The known difference in metabolic endotoxemia between obese and healthy adults was used to predict an expected 50% improvement by GTE treatment. Based on a linear model with treatment and health status, we will have >90% power to detect the primary contrast of interest (GTE vs. placebo in obese individuals) and additionally 80% power to detect an interaction between treatment and health status ($\alpha=0.05$). Thus, we plan to recruit 20 obese and 20 healthy adults for our study. Data from this investigation are expected to be normally distributed or achieved through appropriate transformation. Most data will be analyzed by repeated measures ANCOVA to consider effects due to health status, gender, GTE treatment, and their interactions. Multivariate regression analysis will be performed to define pairwise correlations between study variables in the presence or absence of potential study covariates. Statistical significance for all analyses will be set at $P < 0.05$.

C. Measurement/Instrumentation

Anthropometric Parameters and Blood Pressure. At screening, participants will rest for 15 minutes prior to determining blood pressure using an automated cuff. BMI will be calculated from height determined from a wall-mounted stadiometer and weight from a calibrated scale. Waist circumference will be assessed at the level of the umbilicus using a nonflexible measuring tape.

Blood/Urine Chemistries. Fasting plasma triglyceride, total cholesterol, and glucose will be measured by clinical assay (Pointe Scientific) at screening and throughout the study. Fasting insulin will be measured by ELISA (ALPCO) during the 4-wk study. Serum alanine aminotransferase (ALT) and urinary creatinine will also be measured throughout the study (Pointe Scientific).

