Diet Assessment. Participants will be instructed to maintain a low-polyphenol diet throughout the study. Participants will record any consumption of polyphenol-rich foods throughout the study (a record sheet will be provided, see *Polyphenol Intake Record* attachment). Participants will be instructed to abstain from polyphenol-rich foods including tea of any kind, coffee, fruits, fruit juices, chocolate, nuts, legumes, and wine (a list will be provided, see *List of Polyphenol-Rich Foods* attachment). Food records (3-d) will be evaluated at wk 0, 2, and 4 using NDSR software and the NCC Flavonoid and Proanthocyanin database to assess energy, nutrient, and flavonoid intakes as we described (19, 71).

Plasma and Urine Catechin and Catechin-metabolites. To assess the absorption, metabolism, and excretion of green tea catechins during the pharmacokinetics trial (wk 0), plasma and urine catechin and catechin-metabolites will be measured by liquid chromatography-mass spectrometry (LC-MS). Green tea catechins (EGCG, ECG, EGC, EC) and their metabolites (e.g. valerolactones) will be measured using an adapted LC-MS method (72).

Metabolic Endotoxemia. Serum endotoxin will be measured at wk 0, 2, and 4 using a commercially available fluorometric assay that assesses endotoxin-mediated activation of recombinant Factor C and subsequent cleavage of a flurogenic substrate (PyroGene rFC; Lonza) as we detailed (43).

Gastrointestinal (GI) Permeability. A 4-sugar probe procedure appropriate for human clinical study will be performed as described (73). In brief, at wk 0 and 4, participants in the fasted state will ingest a 500-mL solution of sucrose (40 g), lactulose (5 g), mannitol (1 g) and sucralose (1 g) dissolved in water. Urine will be collected over a 24-hour period to assess GI permeability. Standardized sucrose-free meals (i.e. plain bagel, cream cheese, scrambled eggs, potato chips) will

be provided during the urine collection duration. Urinary sugars will be measured by LC-MS and permeability calculated as urinary excretion (%) and excretion ratios for sugars from 0-5 hours and 6-24 hours to reflect upper and lower GI permeability, respectively (74-77).

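### Repeated measures ANCOVA, with no rule for incomplete data or analysis set, may discard partial endotoxin data that a mixed model in all randomised participants would keep; the gain is real but modest

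*Combined protocol and SAP*

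**What the plan says.** Section III.B (Power Calculation and Data Analysis) fixes the primary outcome: "A power calculation was performed using serum endotoxin (lipopolysaccharide; LPS) as the primary outcome". The primary contrast is GTE against placebo in obese participants, with power put above 90%, and "additionally 80% power to detect an interaction between treatment and health status". On size: "we plan to recruit 20 obese and 20 healthy adults for our study". On method: "Most data will be analyzed by repeated measures ANCOVA to consider effects due to health status, gender, GTE treatment, and their interactions".

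Section III.C (Metabolic Endotoxemia) gives the schedule: "Serum endotoxin will be measured at wk 0, 2, and 4". That is one baseline and two post-baseline readings.

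Section III.D (Privacy/Confidentiality) foresees withdrawal, since participants are told that "they may withdraw at any time without prejudice". Section III.D (Intervention Phase / Test Confections) assesses compliance from returned confections, but does not say whether poor compliers stay in the analysis.

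The documents name no covariance structure, missing-data rule, analysis population, dropout allowance or replacement rule. They also give no allocation ratio and no primary time point for endotoxin.

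**The concern.** Repeated measures ANCOVA in its usual form works on one complete row per person. A participant with weeks 0 and 2 but not week 4 contributes nothing, although the week-2 value is valid on-treatment information. In a contrast of about 10 against 10, every lost row is felt, and the number to be recruited equals the number behind the power statement.

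Two things are at stake. One is precision, because usable readings are thrown away. The other is the analysis set: a completers-only comparison is no longer the randomised one, and it can be biased if leaving depends on early response or on tolerating the product. Because no rule is written, the set could also be settled after the data are seen.

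**Working it through.** **Inputs from the documents.** 20 obese and 20 healthy participants, two arms, endotoxin at weeks 0, 2 and 4, power above 90% (primary contrast) and 80% (interaction), significance level 0.05.

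**Assumptions.** 1:1 allocation within health status (10 per cell), two-sided test, 5, 10 or 15% missing per post-baseline visit, and equal within-person correlation of 0.5 or 0.6. The plan gives no SD or absolute difference, so its power figures cannot be reproduced. Only their mutual consistency can be tested.

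**Step 1: effect implied by the stated power.** With n per cell and df = 4n - 4, the standard error in SD units is √(2/n) for the primary contrast and √(4/n) for the interaction. At n = 10 these are 0.447 and 0.632. By noncentral t, 80% interaction power needs 1.82 SD (noncentrality 1.82/0.632 = 2.88). If GTE does nothing in healthy adults, the obese contrast is also 1.82 SD, with noncentrality 1.82/0.447 = 4.07 and power 97.7%. This agrees with the stated figure of more than 90%.

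**Step 2: power as complete rows fall, at 1.82 SD.**

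| Complete rows per cell | Primary contrast | Interaction |
|---|---|---|
| 10 | 97.7% | 80.0% |
| 9 | 96.3% | 75.4% |
| 8 | 94.0% | 70.1% |
| 7 | 90.4% | 63.7% |

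**Step 3: how many rows are lost.** With independent misses at rate m, complete rows are (1 - m)²: 90, 81 and 72%. That loses 2.0, 3.8 and 5.6 of the 20 obese participants. If all losses follow week 2 and are permanent, complete rows are 1 - m: 95, 90 and 85%, a loss of 1, 2 and 3.

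**Step 4: what a mixed model recovers (large-sample, baseline-adjusted).** After adjustment for baseline, each post-baseline reading has variance 1 - ρ² and the two have covariance ρ - ρ². For ρ = 0.5 these are 0.75 and 0.25, and the inverse matrix has 1.5 on the diagonal and -0.5 off it. Take m = 10%.

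- *Independent misses, week-2/4 mean.* Full-data variance is (0.75 + 0.25)/2 = 0.5. Complete-case variance is 0.5/0.81 = 0.617. Mixed-model information is 0.81 × 1.5 + 0.09/0.75 = 1.335 on the diagonal and -0.405 off it, so the variance is 1/[2 × (1.335 - 0.405)] = 0.538. The standard error ratio is √(0.617/0.538) = 1.07.
- *Loss after week 2, week 4 alone.* Complete-case variance is 0.75/0.9 = 0.833. Mixed-model information is 1.483 (week 2) and 1.35 (week 4), with -0.45 off the diagonal, so the week-4 variance is 1.483/(1.483 × 1.35 - 0.2025) = 0.824. The ratio is √(0.833/0.824), about 1.006.
- *Loss after week 2, week-2/4 mean.* Complete-case variance is 0.5/0.9 = 0.556 and mixed-model variance 0.519. The ratio is 1.035.

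Over m = 5-15% and ρ = 0.5-0.6, the complete-case standard error is larger by:

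| Pattern of loss | Excess over mixed model |
|---|---|
| Independent misses | about 3-11% |
| All after week 2, week-2/4 mean | about 2-6% |
| All after week 2, week 4 alone | about 0.3-1% |

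**Step 5: bias.** In a severe assumed scenario, GTE participants with above-average week-2 endotoxin leave at 40%, other GTE participants at 5% and placebo participants at 10%, with correlation 0.6. In 6,000 simulated trials, completers show a false benefit of 0.08 SD on the week-2/4 mean and 0.04 SD at week 4. Against 1.82 SD that is 0.08/1.82 = 4% and 0.04/1.82 = 2%. Using all available readings, it is about zero.

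**The case against.** **Deletion is not planned.** A reader might infer that the plan commits to dropping incomplete participants. It does not: no deletion rule or software is named, and the same label could be fitted as a mixed model. This stands. What can be said is that the conventional form deletes and nothing in the plan prevents it.

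**The primary contrast is not in danger on the plan's own terms.** A reader might set the primary contrast at exactly 90% power (1.49 SD at 10 per cell) and see it fall to 87/82/76% at 9/8/7 per cell. That does not fit the plan, which claims 80% for the interaction at the same sample size. Unless GTE acts in the opposite direction in healthy adults, that implies at least 1.82 SD in the obese. This stands; the exposed figure is the interaction.

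**Independent misses are less plausible than permanent loss.** Section III.D hands out the second two-week supply at the week-2 visit, so someone who skips it would not normally continue to week 4. This largely stands, although a single failed sample or assay remains possible.

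**Burden falls mostly before treatment.** The 12-hour session, first sugar probe test and first stool collection precede the intervention. Someone who leaves then has no post-baseline reading, and no model recovers treatment information from them. This stands.

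**The time point is open.** If week 4 alone were primary, a missed week-2 reading would remove nobody. This also stands, but the method named is a repeated measures one, so the point is not answered by it.

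**Scope.** Repeated measures ANCOVA is assigned to most data, not all: section III.C gives microbiota to multivariate techniques. Outcomes read only at weeks 0 and 4 gain essentially nothing from a mixed model.

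**Conclusion.** The concern holds, at modest size. The named method, in its conventional form, wastes partial data on the primary outcome, and the plan neither keeps those data nor defines who is analysed. A mixed model in all randomised participants is the better choice and costs almost nothing.

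The precision gain depends on the pattern of loss: appreciable if misses are scattered, and very small at week 4 if people leave for good after week 2. The fall in interaction power cannot all be charged to the method, since a mixed model recovers only part of it. Bias from informative dropout is small even in a severe scenario, so the documents do not support a claim that the trial's main comparison would be seriously distorted or lose its stated power.

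All sizes rest on assumed missingness, correlation, 1:1 allocation and, for power, no GTE effect in healthy adults.

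**What to change.** In section III.B, for serum endotoxin and other outcomes with readings at both week 2 and week 4, replace repeated measures ANCOVA with a linear mixed model fitted by REML, with unstructured covariance over visits and Kenward-Roger degrees of freedom. State that:

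- all randomised participants are included as allocated, with every available reading, whatever their confection count;
- the number of readings is reported by arm and visit;
- a completers-only fit is kept as a sensitivity analysis.

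Outcomes read only at weeks 0 and 4 can stay with baseline-adjusted ANCOVA, analysed as allocated. Settle this wording before the codes are broken (section III.E).

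The cost is slightly more analysis work: no new data or visits, and standard software. With complete data the result should be close to that of the planned method. The mixed model assumes that data are missing at random, and it cannot recover treatment information from anyone who leaves before week 2.

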NAFLD is the most prevalent liver disease in the U.S. affecting 80-100 million Americans (64), which is largely associated with obesity and type 2 diabetes (6, 10-14, 65). Although several mechanisms are involved in the development of NASH from NAFLD, metabolic endotoxemia due to increased gut barrier permeability and alterations in gut microbiota are highly implicated. Findings of this application are expected to provide the first evidence using a novel GTE-rich confection (i.e. snack food) to assess catechin pharmacokinetics in association with improvements in metabolic endotoxemia, gut permeability, and gut microbiota composition to improve gut health, otherwise

impaired in obese individuals. Thus, GTE-mediated improvements in obese subjects are expected to provide support for future translational studies in NASH patients.

III. Procedures

A. Research Design

We will conduct a randomized, double-blind placebo controlled trial in obese and healthy individuals. We will enroll overweight/obese ($BMI = 28-40 \text{ kg/m}^2$) and age- and gender-matched healthy ($BMI 19-24 \text{ kg/m}^2$) men and women (18-50 y; $n = 20/\text{group}$). Participants will be block randomized to receive GTE-rich (1 g GTE) or placebo confections and will be asked to consume the confections daily for 4 wk. Prior to (0 wk) and following 4-wk intervention, we will collect fasting blood, 24-hour urine, and 3-d fecal samples. Additionally, at the beginning (0 wk), participants will perform a sugar probe test to assess gut permeability and a 12-h pharmacokinetics trial to assess green tea catechin absorption, metabolism, and elimination. At the end of the intervention (4 wk), participants will perform a second sugar probe test to assess gastrointestinal changes associated with chronic GTE supplementation. Blood collected at wk 0, 2, and 4 will be used to assess blood chemistries (i.e. liver function, glucose, insulin, insulin resistance, markers of inflammation). In addition, blood pressure, anthropometrics, and 3-d diet records will be measured and collected.

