Enrollment Criteria. Overweight/obese men and women are the ideal study population because of its close association with NASH (6, 10-14, 65). Obese/overweight participants will be required to meet these **inclusion criteria**: a) overweight/obese ($BMI = 28-40 \text{ kg/m}^2$), b) 18-50 y of age, c) fasting glucose $< 126 \text{ mg/dL}$, d) normotensive (blood pressure $< 140/90 \text{ mmHg}$), e) non-dietary supplement user, f) nonsmoker. We will also enroll age- and gender-matched healthy adults who meet the following criteria: a) normal weight ($BMI 19-24 \text{ kg/m}^2$), b) 18-50 y of age, c) normoglycemic ($< 100 \text{ mg/dL}$), d) normolipidemic (total cholesterol $< 240 \text{ mg/dL}$ and triglyceride $< 150 \text{ mg/dL}$), e) normotensive (blood pressure $< 140/90 \text{ mmHg}$). Those having any of these **exclusion criteria** will not be enrolled: a) regular tea drinkers (*Camellia sinensis* or herbal varieties; ≥ 2 cups/wk), b) vegetarians, c) use of any medications to manage diabetes, hypertension, or hyperlipidemia (e.g. statins, metformin, ACE inhibitors), d) use of any medications known to be contraindicated for use with green tea ingestion (e.g. antipsychotic medications [Clozapine, lithium, Diazepam]), blood

thinning medications [Warfarin]), e) user of dietary supplements, prebiotics or probiotics, f) recent use of antibiotics or antiinflammatory agents, g) women who are pregnant or lactating, or have initiated or changed birth control in the past 3-months, h) individuals with any gastrointestinal disorders or surgeries, i) hemochromatosis, j) alcohol intake > 3 drinks/day, k) any history of cancer.

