The participant will be instructed to abstain from exercise for 24 hours prior to their sugar probe test and pharmacokinetics trial. For each visit to our study center, participants will be instructed to be fasted for 10-12 hours to ensure reliable blood sampling. Participants will be instructed to complete the dietary record for 3-d before the pharmacokinetics trial and second sugar probe test (wk 0 and 4) and their wk 2 study center visit.

Test Trials. Participants will be block randomized into two groups to receive either a GTE-rich or placebo (without GTE) confection. Participants will complete a pharmacokinetics trial prior to starting the intervention. Prior to (wk 0) and following 4-wk intervention, participants will collect 3 days of fecal samples and complete a sugar probe test. For this study, each participant will visit the study center a total of 6 times, including the screening and dietary meetings, to complete individual test trials. For each study center visit, participants will report in a fasted state (10-12 hours).

Prior to the first study visit, participants will complete a 3-d diet record. At the first study visit, participants will perform a sugar probe test. This test will consist of participants ingesting a test beverage of 40 g sucrose, 5 g lactulose, 1 g mannitol, and 1 g sucralose dissolved in water (500 mL). After ingestion, the participants will be provided a standardized sucrose-free meal within the first 5 hours and water throughout. Urine will be collected from 0-5 and 6-24 hours in provided containers.

The second study visit will be scheduled at least 3 d after the sugar probe test. The second study visit will consist of a 12-h pharmacokinetics trial. Participants will ingest one-half the daily GTE-rich confections (0.5 g GTE). Blood will then be collected at the following hourly time points: 0 (before confection ingestion), 0.25, 0.5, 1, 2, 3, 5, 8, 10, 12 h. Urine will be collected between 0-4, 4-8, 8-12, and 12-24 h post-ingestion into provided urinary collection containers. During the pharmacokinetics trial, participants will be allowed free access to water and provided a standardized-polyphenol free meal.

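### Healthy controls are matched on age and gender, but the stated model names gender and not age, which matters for the non-randomised obese-versus-healthy comparisons if age predicts the outcome

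*Combined protocol and SAP*

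**What the plan says.** The matching appears twice. Section III.A (Research Design) describes the controls as "age- and gender-matched healthy" men and women, and III.B (Enrollment Criteria) states "We will also enroll age- and gender-matched healthy adults who meet the following criteria". Both groups span 18-50 years. No caliper, matching ratio or pairing rule is given.

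The analysis is in III.B (Power Calculation and Data Analysis), where most of the data go into a repeated measures ANCOVA "to consider effects due to health status, gender, GTE treatment, and their interactions". Gender is named and age is not. There is no term for a matched set, and no continuous covariate is listed for the ANCOVA. Covariates come up only in the next sentence, unnamed and for a different analysis: "Multivariate regression analysis will be performed to define pairwise correlations between study variables in the presence or absence of potential study covariates".

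Age is already collected (III.B, Recruitment). The same section names GTE versus placebo in obese participants as the primary contrast, with serum endotoxin as the primary outcome.

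**The concern.** Block randomisation to GTE or placebo does nothing to balance age between obese and healthy participants. For that comparison, matching and adjustment are the only protections, and the plan leaves the second one open for age.

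Two things follow if age is related to the outcome. First, matching removes age differences between the groups, but the variation due to age stays in the residual unless the model contains age. The computed standard error is then larger than the true sampling error, and the precision gained by matching is not used. Second, if matching is loose, part of an obese-versus-healthy difference is an age difference, and nothing in the stated model takes it out.

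The comparisons affected are Objective 1 (catechin pharmacokinetics by health status) and the baseline contrasts in endotoxin, gut permeability and microbiota that the protocol expects under Anticipated Results.

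**Working it through.** **Inputs from the documents.** The plan says "we plan to recruit 20 obese and 20 healthy adults for our study". Allocation: "Participants will be block randomized into two groups to receive either a GTE-rich or placebo". "Statistical significance for all analyses will be set at" P < 0.05. Ages run from 18 to 50.

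**Assumptions.** 1:1 allocation (10 per health-by-treatment cell), two-sided testing, equal gender split, ages uniform over 18-50, a linear age effect, and a within-cell age-outcome correlation r from 0 to 0.5.

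**1. The plan's power figures.** They cannot be reproduced, because neither an SD nor an absolute difference is given. They can be checked against each other. In SD units, the standard error is √(2/10) = 0.447 for the primary contrast and √(4/10) = 0.632 for the interaction. If GTE has no effect in healthy adults, 80% power for the interaction needs an effect of (1.960 + 0.842) × 0.632 = 1.77 SD (normal approximation). The same effect gives 97.7% power for the primary contrast, which agrees with the stated >90%. That power model contains treatment and health status only, so whether age enters the obese-versus-healthy analyses does not alter either figure.

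**2. Interval width with age added.** A health status × gender × treatment model has 8 cells, so 40 − 8 = 32 error degrees of freedom, or 31 with age. The ratio of 95% half-widths (with age / without age) is

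√(1 − r²) × √f × t(31)/t(32), where t(31)/t(32) = 1.0013.

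Here f = 1 when ages are closely matched and 1 + 1/30 when matching has no effect. Example at r = 0.3, close matching: √0.91 × 1.0013 = 0.955.

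| r | closely matched | no effective matching |
|---|---|---|
| 0 | 1.001 | 1.018 |
| 0.1 | 0.996 | 1.013 |
| 0.2 | 0.981 | 0.997 |
| 0.3 | 0.955 | 0.971 |
| 0.5 | 0.867 | 0.882 |

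**3. Bias from a leftover age gap.** The SD of age is 32/√12 = 9.24 years. Bias in outcome SDs = r × gap / 9.24. For an assumed 3-year mean gap:

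- r = 0.1: 0.03 SD
- r = 0.3: 0.10 SD
- r = 0.5: 0.16 SD

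The standard error of the 20 versus 20 contrast is √(2/20) = 0.316 SD, so the bias is about 10%, 31% and 51% of a standard error. For scale, if matching had no effect, the standard error of the mean age gap would be 9.24 × 0.316 = 2.9 years, so a 3-year gap would then be unremarkable. Effective matching would make it smaller.

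**4. Simulation (3,000 trials per scenario, n = 40).** It agrees with steps 2 and 3. With controls within 2 years and r = 0.5, the mean half-width falls from 0.644 to 0.558 (ratio 0.867). Without age, coverage is 97.9% (97.6% when matched within 5 years). With age it is 95.5% (95.2%). With a 3-year gap, the simulated bias without age is 0.035, 0.097 and 0.156 SD at r = 0.1, 0.3 and 0.5. With age it is within 0.01 SD of zero.

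**The case against.** The case for leaving the plan alone has five parts.

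- **An ANCOVA implies covariates.** The sentence lists effects of interest for most of the data and need not be the whole model. This stands in part: age is unspecified, not ruled out. But no covariate is named, and the sentence that mentions covariates concerns a correlation regression.
- **Nothing shows that age matters here.** The documents give no correlation of age with endotoxin, catechins, permeability or microbiota. This stands. A reader might infer that the planned intervals are known to be 5-15% too wide. That range needs r of roughly 0.3 to 0.5. At r of 0.2 or less with close matching the gain is about 2% or less, and with ineffective matching and r near zero, adding age widens the interval slightly.
- **Mismatch is possible but not shown.** This also stands. The Screening Meeting text lets participants who narrowly miss criteria be admitted, and a reader might take that as loosening the age match. The clause concerns inclusion and exclusion criteria, its example is a BMI, and it says nothing about matching. What remains is that no caliper is stated.
- **The error is on the safe side.** With close matching the planned interval over-covers, which costs efficiency and creates no false positives. This is correct for width. It does not cover the bias from an age gap.
- **The main result is untouched.** This is correct. Age is also constant within a person, so an age main effect does not change the within-person error for change over weeks 0, 2 and 4.

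**Conclusion.** A minor point that holds conditionally. One of two matching factors is missing from the only stated model, nothing replaces it, and the comparisons that rely on matching are the non-randomised ones. If age predicts the outcome and matching is close, those intervals are conservative: including age would narrow them by less than 5% for r up to 0.3 and by 13% at r = 0.5. If matching is ineffective, the planned interval has about the right coverage but is less precise than it could be once r is above about 0.2. Any leftover age gap goes uncorrected. At an assumed 3 years the bias is at most about half a standard error over the range of r considered.

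A reader might go further and conclude that the primary endotoxin result is biased or underpowered for this reason. The documents do not support that: the primary contrast is randomised within obese participants, matching to healthy controls plays no part in it, and the power figures were derived without age.

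The sizes rest on the assumed correlations, uniform ages, a linear age effect, 1:1 allocation and equal gender split.

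**What to change.** In III.B (Power Calculation and Data Analysis), state that every comparison of obese with healthy participants, including the pharmacokinetic one, will include age in years as a continuous covariate alongside gender. Settle this before outcome data are analysed, so that adjusting for age is not a choice made after seeing results. In Enrollment Criteria, say how age matching is done (caliper, and whether controls are paired individually). Add a matched-set term only if controls are actually paired; no section says that they are.

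The cost is a sentence in each place and no new data. The statistical price is 1 of about 32 error degrees of freedom in the health status × gender × treatment model. If age turns out to be unrelated to the outcome, the intervals are 0.1% wider with close matching and 1.8% wider with none. The randomised primary contrast does not need this change.
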